6.5 Risks and benefits

Participants for this study will be selected on the basis that they have a diagnosis of colon cancer that requires surgical resection, and are suitable for segmental colectomy with D3 lymphadenectomy. There will be the normal risk of surgical complications associated with general anaesthesia and surgical resection. There is a small risk of photosensitivity reactions related to 5-ALA administration. This includes transient derangement of liver function tests (returning to baseline at 24 – 72 hours post-administration) and skin hypersensitivity reactions due to exposure to UV-light. Other mild and transient side effects associated with 5-ALA administration include nausea, vomiting, tachycardia, and hypotension. When 5-ALA is administered in conjunction with surgical resection of malignant brain tumours, a potential side effect is brain oedema. In response to these potential adverse effects, all patients will be kept out of direct sunlight for at least the first 48 hours following

surgery and monitored for changes in vital signs and liver function (this is normal postoperative care). During the operation patient's eyes and skin will be protected from the operating lights, using standard methods such as sterile drapes and tape to keep their eyes closed.

The above risks to patients will be offset by the advantages arising from taking part in the study. These include potential benefits arising from laparoscopic surgery that is of high quality and scrutinized by pathological assessment, high calibre histopathological analysis of the resection specimen and in particular the lymph node status, and close monitoring during the postoperative period.

The main beneficiaries, should 5-ALA fluorescence diagnosis prove to be effective, will be future generations of colon cancer sufferers. The ability to accurately tailor the radicality of surgery to the stage of the primary cancer should enable optimal oncological resection whilst minimizing the risk of unnecessary postoperative morbidity.

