The reasons for the selective uptake of 5-ALA in tumour cells have not been fully elucidated. In normal cells, 5-ALA synthesis is regulated by a feedback control system that is driven by high intracellular concentrations of free heme. This system is overridden when exogenous 5-ALA is administered. Accumulation of PpIX in tumour relative to normal cells has been attributed to alterations in the activity of the rate limiting enzymes porphobilinogen deaminase (PBGD) and ferrochelatase (FC) (24, 25). The former is increased and the latter decreased in tumour cells. Alterations in enzymatic activity may also be due to reduced availability of intracellular Fe2+ as a result of rapid cell division. Additionally, several biochemical and structural changes in tumour cells have been linked to their avidity for PpIX, including reduced pH, up-regulation of low-density lipoprotein receptors, and stromal abnormalities including large interstitial space, leaky vasculature, and large amounts of newly synthesised collagens and lipids (26).

Following systemic administration, 5-ALA is metabolised in the liver and excreted in the bile and urine. Much of the 5-ALA is used by the liver to synthesize PpIX, whilst the remaining 5-ALA circulates to other body sites where all other cell types (except those without mitochondria) convert it to PpIX. Intracellular PpIX returns to normal levels up to 48hrs post application.

A substantial body of work has accumulated on the use of 5-ALA and its derivatives in the fluorescence detection of solid cancers. In humans, 5-ALA fluorescence has been extensively used as a diagnostic aid in transitional cell carcinoma of the bladder (26), in neurosurgery to guide malignant glioma resection, and in gynaecology to detect endometriosis (27, 28), peritoneal metastases from ovarian cancer (29) and cervical squamous intraepithelial lesions (30).

In Urology, several studies have shown the superior detection of transitional carcinoma of the bladder using photodynamic diagnosis as compared to white light cystoscopy. Both 5-ALA and its hexyl-derivative, Hexaminolaevulinate (HEX), have been evaluated in bladder cancer. Burger et al reported reduced residual tumour

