duodenum, and colon, patients were administered 30-60 mg/kg 5-ALA by the oral route (36). In colorectal cancer patients, flexible sigmoidoscopy was performed with serial biopsies. Peak fluorescence in the large bowel tumours was achieved within 6 hours, with good selectivity between tumour and normal mucosa at a ratio 5:1. Similarly effective results were seen in oesophageal and duodenal lesions, but with a lower dose of 30mg/kg 5-ALA.

An important issue with the clinical use of any photosensitizing agent is the potential for side effects. This problem appears to be confined to systemic administration when high doses are used for photodynamic therapy as opposed to lower doses used in fluorescence diagnosis. When used systemically, it is important to establish a safe dose of photosensitiser according to the interval drug to light time to avoid photosensitivity side effects. Normal precautions include keeping the patient out of direct sunlight for 24-48 hours following drug administration. Occasionally reported side effects following systemic administration include nausea, vomiting, tachycardia, hypotension, photosensitivity for up to 48 hours, and elevated liver enzymes (25). A recent trial involving 351 patients given oral 5-ALA (20mg/kg) prior to fluorescent glioma resection showed no difference in the number of adverse events between patients given 5-ALA and those who didn't receive it (37). Following systemic administration 5-ALA is associated with a transient rise in aspartate transaminase and bilirubin levels, which return to normal after 72 hours.

In a study examining the clinical pharmacokinetics of 5-ALA in normal healthy volunteers and patients at high risk of recurrent bladder cancer the peak plasma concentration of 5-ALA following oral administration were achieved at $0.83 \pm 0.20h$. Plasma 5-ALA concentrations declined with a terminal half-life of approximately 45 minutes (38).

Proposed strategy for 5-ALA intraoperative lymph node detection

We aim to combine existing techniques in SLN mapping using colorimetric dyes, to

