12.1 Investigational Medicinal Products

The following are classified as Investigational Medicinal Products (IMPs).

• 5-ALA

5-ALA (in the form of its hydrochloride, 5-ALA HCI) has been used in humans for fluorescence diagnosis and photodynamic therapy in a variety of cancers. It preferentially accumulates in cancer cells where it is metabolised to Protoporphyrin IX (PpIX), a component of the Heme pathway and an endogenous photosensitiser (22).

5-ALA is safe for human administration; it is used topically in dermatological malignancies, intravesically to detect bladder cancers, and orally in premalignant oesophageal lesions and malignant gliomas (23). It has also been administered intradermally, intraperitoneally and intravenously in experimental studies without adverse effects. 5-ALA is available in various forms depending on the intended mode of application. When administered orally in high doses for photodynamic therapy, side-effects may include nausea, tachycardia, hypotension, photosensitivity, and a transient rise in aspartate transaminase and bilirubin When 5-ALA is administered orally in conjunction with surgical resection of malignant brain tumours side effects can include brain oedema. 5-ALA is cleared by the liver and kidneys with a short half-life and return to baseline levels by 24 hours. Much smaller doses are required for fluorescence diagnosis; typically 20 mg/kg.

Please refer to the Pharmacy and IMP Trial Site Operating Procedure for full details of the trial IMP management requirements, including details of IMP labelling,

destruction, accountability and disposal records.

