12.5 Concomitant Medications

The only absolute contra-indications to the use of 5-ALA are

- A previous history of hypersensitivity to photosensitising drugs
- A previous history of acute or chronic porphyria
- Hepatic or renal dysfunction
- Pregnancy

5-ALA should be used with caution:

- With other medications known to have a photosensitising effect e.g. tetracylines, sulphonamides, quinolones. Patients should not be exposed to any photosensitizing agent up to 2 weeks after administration of 5 ALA
- With other medications associated with acute porphyria e.g. diclofenac, barbiturates, carbamazepine, phenytoin
- With other medication associated with hepatic or renal dysfunction e.g. NSAIDs, ACEinhibitors, loop diuretics, phenytoin

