15.3 Study Definitions

• Standardisation of operative procedure including D3 lymphadenectomy will be achieved through the production of a training video to standardise segmental right and

sigmoid colectomy with D3 lymphadenectomy.

- Patient factors affecting the accuracy of 5-ALA fluorescence diagnosis will be identified and recorded e.g. BMI and visceral obesity.
- Safety will be assessed by review of:
 - adverse events from the time of colonoscopic application of colorimetric dye and oral administration of 5-ALA to 30 days post-operatively,
 - ii) intra-and post-operative complications and mortality up to 30 days and re-operation rate

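### Sunlight avoidance is counted from surgery, not from the 5-ALA dose, so the 4-6 h before operation and any postponed operation have no written light precaution

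*Protocol*

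**What the plan says.** Section 6.5 names skin reactions to UV light among the risks of 5-ALA and sets out the response in one sentence. Its first half is the sunlight rule: "all patients will be kept out of direct sunlight for at least the first 48 hours following" surgery. Its second half is monitoring: "surgery and monitored for changes in vital signs and liver function (this is normal postoperative care"). Section 6.5 also has the eyes and skin shielded from the operating lights during the operation.

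Section 11.1.2 has participants admitted to hospital and given oral 5-ALA 4-6 h before operation. It contains no light instruction.

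Section 6.4, in the background on photodynamic diagnosis, uses a different starting point: "Normal precautions include keeping the patient out of direct sunlight for 24-48 hours following drug administration". It also says of the fluorescent metabolite: "Intracellular PpIX returns to normal levels up to 48hrs post application".

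**The concern.** Photosensitivity comes from the drug, so a precaution against it should start when the drug is taken. The rule in Section 6.5 starts at a later event, and one that may not happen on the day. Two situations are left without a written instruction.

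- **Every patient, from dose to operation.** No section shown states a light precaution for this interval.
- **A dosed patient whose operation is postponed or cancelled.** A rule counted from surgery then never starts, although the patient has had the full dose and could leave the ward.

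What is at stake is a small point of patient safety. No endpoint, analysis or progression criterion depends on it.

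**Working it through.** The protocol gives no figure for this gap, so the check is a timeline built from its own numbers.

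**Inputs**

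- Dose to operation: 4-6 h (Section 11.1.2).
- Trial sunlight rule: at least 48 h, counted from surgery (Section 6.5).
- Shielding of eyes and skin: during the operation (Section 6.5).
- Usual precaution: 24-48 h, counted from the drug (Section 6.4).
- Metabolite back to normal: up to 48 h after application (Section 6.4).

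**Cover as written, in hours after the dose**

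| Period | Hours after dose | Written light precaution |
|---|---|---|
| Dose to operation | 0 to 4-6 | None |
| Operation | from 4-6 | Eyes and skin shielded |
| After surgery | to at least 52-54 | Sunlight avoided |
| Dosed, no operation | 0 onwards | None |

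**Start of cover.** The uncovered time equals the dose-to-operation interval, 4-6 h. As a share of the usual precaution counted from the drug:

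- against 48 h: 4/48 = 8.3% and 6/48 = 12.5%;
- against 24 h: 4/24 = 16.7% and 6/24 = 25%.

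**End of cover.** 48 + 4 = 52 h and 48 + 6 = 54 h after the dose, and later if the count runs from the end of the operation. Both exceed the 48 h in Section 6.4, so the end needs no change.

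**Postponed or cancelled operation.** The start of the rule is undefined, so none of the 24-48 h is covered by a written instruction.

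**With the rule counted from dosing.** The uncovered 4-6 h becomes 0 h, and a patient who is not operated on has at least 48 h of cover.

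**The case against.** The strongest reply is that the gap has little practical content. Patients are inpatients awaiting theatre, so strong sunlight is unlikely. Section 6.4 plays down the side-effect risk at diagnostic doses: "This problem appears to be confined to systemic administration when high doses are used for photodynamic therapy". Sections 12.1 and 12.2 refer IMP management details to a separate operating procedure that is not shown and may carry a light instruction. The Section 6.4 sentence on sunlight is background, so the protocol does not hold two conflicting trial instructions. All of this stands, and it sets the low priority. It does not remove the point, because Section 6.5 chose to state a rule, and that rule starts at the wrong event. The postponed-operation case is not met by the inpatient argument, although nothing in the protocol says how often it would arise.

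The two-week limit in Section 12.5, "Patients should not be exposed to any photosensitizing agent up to 2 weeks after administration of 5 ALA", also counts from the drug, but it concerns other photosensitising agents. It is only weak support.

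A reader might infer something stronger from the second half of the Section 6.5 sentence: that nausea, vomiting, tachycardia or hypotension before surgery would go unmonitored or unrecorded. The documents do not support that:

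- Section 14.2 collects adverse events from registration, including those found by questioning or examination.
- Section 15.3 defines the safety review to include "adverse events from the time of colonoscopic application of colorimetric dye and oral administration of 5-ALA to 30 days post-operatively".
- Section 13.2 leaves general pre-operative assessment to institutional protocol, and the full case report forms are not shown.
- The plasma peak in Section 6.4 (0.83 ± 0.20 h after the dose) does fall before the operation, but the protocol gives no onset times for these effects.
- The dense observations in Section 13.6 are routine recovery care after colectomy, so they are no yardstick for the hours before it.

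**Conclusion.** The point holds as a correction to one stated rule. As written, the light precaution misses the first 4-6 h after dosing and does not apply to a dosed patient who is not operated on. It is a low-priority, inexpensive improvement to patient safety.

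The conclusion assumes that the text of Section 6.5 is followed literally and that no document outside the protocol already supplies the missing instruction. The protocol gives no rate of skin reactions at 10-30 mg/kg and no rate of postponement, so no risk figure is offered. The documents do not establish a deficiency in adverse event capture or in pre-operative observations.

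**What to change.** In Sections 6.5 and 11.1.2, state that light precautions start at 5-ALA administration and continue to at least 48 h after surgery, or to at least 48 h after dosing if the operation does not go ahead.

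Optionally, note any vomiting after the oral dose beside the dose and time that Appendix 4 already records. A lost dose could help to explain absent fluorescence, which bears on the second secondary objective in Section 7.2.

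The cost is one line of text in each section and a negligible ward burden.

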7 AIMS AND OBJECTIVES

The purpose of this study is to optimise the use of 5-ALA for intra-operative fluorescence diagnosis (FD) of metastatic lymph nodes in colon cancer. We hypothesize that 5-ALA FD provides an accurate means of intraoperative lymph node staging and that it is more accurate than preoperative CT staging.

7.1 Primary Objective

• To optimize the dose and timing of oral 5-ALA administration for intraoperative fluorescence diagnosis of metastatic lymph nodes in colon cancer.

7.2 Secondary Objectives

1. Establish a reliable and repeatable methodology for fluorescence diagnosis of

lymph node metastasis by standardisation of:

- i) pre-operative CT lymph node reporting
- ii) intra-operative fluorescence detection system
- surgical technique for laparoscopic segmental colonic resection and with D3 lymphadenectomy
- iv) histopathogical examination of resected specimens.

2. Identify systemic, operative and patient factors, which adversely affect the intraoperative detection of lymph node fluorescence.

8 DESIGN

8.1 Study Design

This developmental study will focus on optimizing the technique of intraoperative lymph node staging using a combination of colorimetric dyes and 5-ALA. Colorimetric dye (India ink) is in routine use for SLN mapping.

Parameters to be optimised during the development phase include:

i) The dose of 5-ALA.

The most effective dose, with best-tolerated adverse effect profile from previous clinical trials, is 20 - 30mg/kg. There is some evidence that doses of 10mg/kg are equally effective. Higher doses up to 40mg/kg have been used with no increase in FD, but a higher incidence of adverse effects. (See Appendix 1 for evidence of current trials using 5-ALA)

ii) The dose and technique of administration of India ink for optimal lymphatic mapping.

Experience will be drawn from previously established sentinel lymph node mapping techniques.

- iii) Standardisation of radiological reporting to include evaluation of preoperative lymph node staging.
- iv) Practicalities involved in the use of the Storz D-Light laparoscopic system in detecting lymph nodes marked with India ink (white light mode) and 5-ALA fluorescence (blue light mode).

Support will be provided by the company and advice sought from urological colleagues who use the same system for transurethral resection of bladder cancers.

- v) Standardisation of the techniques for segmental colectomy with D3 lymphadenectomy between the 2 centres involved in the development phase.
- vi) Optimisation and standardisation of the techniques for pathological lymph node mapping and step sectioning for histological lymph node staging.
- viii) Assessment of patient factors that might influence colorimetric and 5-ALA intra-operative lymph node detection, such as advanced versus early tumours, presence of other colonic pathology, patient body mass index etc.

The findings from this preliminary study will feed directly into the trial protocol of the subsequent multicentre evaluation phase. The developmental work will also result in detailed guidance and training videos to limit any operator effect when the technique is used in other trial centres.

Initially two cohorts of 10 patients with positive lymph nodes (as verified on postoperative histology) will be treated with different doses of 5-ALA. As lymph nodes can only be verified on post-operative histology it is anticipated that up to 16 patients may need to be treated to identify 10 with positive lymph nodes. As previously stated, we will attempt to enrich the study population to contain patients

Page | 31

with lymph node disease, but it is emphasised that this cannot be done accurately on preoperative CT staging. As a result, more than 10 patients may have to be recruited to each cohort to achieve the required 10 with positive lymph node disease. Sixteen patients per cohort have been anticipated as there is only 25% -30% lymph node positivity in colorectal cancer. With enrichment of recruitment, to include more lymph node positive patients using the FOxTROT radiology criteria, we estimate that 10 out of 16 patients will be informative with positive lymph nodes. In patients without lymph node disease, fluorescence of the primary cancer will act as a positive control of efficacy of 5-ALA FD of colorectal cancer. Table 1 below provides a guide to the doses that may be used. The two participating centres will work together in this regard, so as to co-ordinate between themselves, but the exact dose administered to each patient will be at the discretion of the treating surgeon. We will start with the predicted optimal dose of administration i.e. 20mg/kg (the most commonly used dose and timing in the literature – Appendix 1). A second cohort will be assessed at a lower dose of 10mg/kg if 20mg gives an indication of activity, or a higher dose of 30mg/kg if 20mg/kg does not give adequate indication of activity. In this way, by the time we have recruited 20 patients with positive lymph nodes we will have optimised the dose of administration.

Tabl	e 1
------	-----

Schedule	5-ALA dose
Cohort 1	20 mg/kg
Cohort 2	10 mg/kg or 30 mg/kg depending on activity
	of 5-ALA at 20 mg/kg

Information will be collected for each dose level including

- toxicity
- 5-ALA identified LN
- Histopathologically confirmed LN status

Within the recruitment of the first 20 patients with positive lymph nodes, the ability of 5-ALA to detect positive nodes as compared to histology in at least 2 of 10 patients (in either cohort) will be required to progress to the next part of the study (see below). This corresponds to the upper bound of the 99% exact confidence interval of the sensitivity being at least 60% i.e. a good indication of activity given that the technical protocols and techniques may not yet be fully optimised. A 99% confidence interval has been chosen to reflect the additional uncertainty in 10 patients.

As the dose of 5-ALA is assessed, work will be carried out to standardise the preoperative radiological assessment, the technique of laparoscopic D3 lymphadenectomy and the pathological lymph node mapping.

If 5-ALA detects positive lymph nodes in at least 2 of 10 patients (in either cohort) then, from these initial results, the most promising dose of 5-ALA will be identified. Both patient and node-level information and practical considerations will be used to further inform this decision. At least a further 10 patients with lymph nodes with metastatic disease as judged by histological evaluation will then be recruited and treated with this schedule, with flexibility to include further patients to confirm the validity of the technique before proceeding to the evaluation phase. The exact number of patients will be determined in discussion with the TSC and DMEC prior to the start of this stage of the trial but, at their discretion, may be increased during this stage of the trial. We will aim to recruit up to 52 patients in total for the developmental phase. However, if necessary, more than this number of patients will be recruited to obtain this number with metastatic disease as judged by histological evaluation. The ability of 5-ALA FD to reliably detect lymph nodes with metastatic disease as judged by histopathological evaluation will be assessed by requiring that, to progress to the evaluation phase, the upper bound of the 99% (Clopper Pearson) confidence interval of the sensitivity (in the patients with positive nodes recruited in this stage of the trial) is at least the target value of 80%. This analysis will be versus histopathology but on a per patient basis, considering whether a patient has at least

1 node identified by 5-ALA. A 99% confidence interval has been used to reflect the additional uncertainty in a relatively low number of patients.

To allow for the optimization of the other variables (e.g. fluorescence detection system), however, this analysis will not include patients treated with this schedule before it was identified as the most promising schedule.

Centres

Two centres will collaborate in the developmental work: [name] (Leeds) and [name] (Dublin). Each centre will recruit patients, aiming to ensure an enriched sample with lymph node metastases. It is anticipated that each centre will recruit 8 patients to each of the initial two cohorts (anticipated total of 16 patients per cohort).

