However, this "one size fits all" approach fails to take into account the biological variation of colon cancer or the fitness and expectations of the patient. Only 25% of cancers have metastatic disease to the lymph nodes, suggesting that D3 lymphadenectomy is overtreatment in the majority. There is the added concern that the majority of colorectal cancer patients are elderly with comorbidity, and that a universal policy of radical resection will lead to unnecessary morbidity. This concern is reinforced by data from the Karolinska Institute, Sweden, with a significant increase in major complications from 19.3% to 28.3% and re-operation rates from

2.9% to 8.6% following the introduction of standardized D3 lymphadenectomy in 2004/5 (personal communication). Other series, however, such as that from Hillerød Hospital, Denmark, have reported improved oncological resection without any increase in morbidity (5). Another factor that needs to be taken into account when determining future surgical strategy is the changing pattern of disease presentation with the introduction of screening programmes. In the UK, the introduction of a national bowel screening programme has seen a shift in incidence of early cancers (Dukes' stage A) from 10.1% prior to screening to 45.3% following implementation (8). As the incidence of lymph node metastases in Dukes' A cancer is less than 10%, a policy of radical D3 lymphadenectomy for all cannot be justified and is unlikely to produce any survival benefit. It therefore seems sensible to adopt a more selective approach whereby patients with lymph node involvement are offered D3 lymphadenectomy, whilst those without nodal involvement undergo a more conventional D2 lymphadenectomy. Currently, there is no reliable method for determining lymph node status either pre-operatively or intra-operatively. The decision to carry out D2 or D3 lymphadenectomy therefore remains at the discretion of the operating surgeon. It is only with an accurate and objective system for intraoperative lymph node staging that the level of resection can be tailored to individual patients. The proposed research will evaluate the merits of 5-ALA fluorescence for this purpose.

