provide an overall lymphatic map, with the tumour-specific properties of 5-ALA fluorescence diagnosis. To our knowledge, this approach has never before been tried. This combination is particularly attractive in the context of laparoscopic surgery with both agents visible with the Storz D-Light Laparoscopic System, which combines white light (colorimetric dyes) and blue light (5-ALA) modes together with enhanced stereoscopic magnification. We will focus on cancers of the right and sigmoid colon and perform segmental colectomy with D3 lymphadenectomy. Resection specimens will be scrutinized using routine and enhanced histopathological methods to determine the sensitivity, specificity, and positive and negative predictive values for 5-ALA fluorescence diagnosis as compared to histological analysis.

In this study, we have chosen to use 5-ALA systemically via oral administration as ranges for the optimal dose and time of preoperative administration in humans have been previously determined (Appendix 1). The supplier of 5-ALA for oral administration will be Photonamic GmbH & Co. Germany.

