15. ENDPOINTS

15.1 Primary Endpoints

 Identification of the optimal dose for oral administration of 5-ALA for the accurate intraoperative detection of lymph node metastases

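### Both progression rules read sensitivity in node-positive patients alone, so a dose with non-specific nodal fluorescence passes them although the primary endpoint is accurate detection

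*Protocol*

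**What the plan says.** The primary endpoint (section 15.1) is the optimal oral dose "for the accurate intraoperative detection of lymph node metastases". Section 6.4 says that the resected specimens will be examined "to determine the sensitivity, specificity, and positive and negative predictive values for 5-ALA fluorescence diagnosis as compared to histological analysis". The clinical reason is in section 6.2: only about a quarter of cancers have nodal metastases, "suggesting that D3 lymphadenectomy is overtreatment in the majority".

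The rules for moving forward are in section 8.1 and are repeated in the synopsis and section 17.1:

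- **First rule.** It requires "the ability of 5-ALA to detect positive nodes as compared to histology in at least 2 of 10 patients (in either cohort"). The reason given is: "This corresponds to the upper bound of the 99% exact confidence interval of the sensitivity being at least 60" per cent.
- **Second rule.** After at least 10 more node-positive patients at the chosen dose, "the upper bound of the 99% (Clopper Pearson) confidence interval of the sensitivity" must reach 80%. It is computed "in the patients with positive nodes recruited in this stage of the trial".

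For node-negative patients, the role that 8.1 states is: "In patients without lymph node disease, fluorescence of the primary cancer will act as a positive control of efficacy".

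Section 8.1 also lets patient-level and node-level information and practical considerations inform the dose choice. Toxicity, fluorescent nodes and histological status are collected at each dose level. Section 15.2 lists patient factors that affect accuracy, but no measure of specificity or of false positives.

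**The concern.** Accuracy has two sides. The test is meant to separate patients who need the wider lymphadenectomy from those who do not, so false positives matter as much to its purpose as missed nodes. A rule computed only in node-positive patients cannot see them. More fluorescence of any kind, specific or not, can only raise the score.

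The per-patient definition of a hit adds to this. The synopsis requires at least one positive tumour node to be identified by 5-ALA. Section 8.1, as printed, requires only at least one node. Read literally, 8.1 lets a fluorescent but uninvolved node count as a detection in a node-positive patient.

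At stake is the yield of the next phase. Section 8.1 says that the findings feed directly into the multicentre evaluation protocol. A dose or detection setting with poor specificity could meet every written criterion here and be recognised only after that larger study has been run.

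**Working it through.** **Inputs.** From 8.1: at least 2 of 10 in either cohort; upper 99% Clopper-Pearson bound at least 80%; at least 10 node-positive patients in the second stage; 10 of 16 expected node-positive; up to 52 patients in total. From 6.3: CT specificity 53% (audit) and 78% (meta-analysis). From Appendix 3: 27 nodes in the worked mapping example.

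**1. The plan's own figure.** The two-sided 99% upper bound for x of n is the 0.995 quantile of Beta(x+1, n−x). At n = 10 it is 54.4% for 1/10 and 64.8% for 2/10. So 2/10 is the smallest count that reaches 60%, and the stated correspondence is right.

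**2. The second rule at n = 10.** The bound is 73.5% for 3/10 and 80.9% for 4/10. The rule is therefore at least 4 of 10.

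**3. Every node fluoresces.** Every node-positive patient is then a hit: 10/10, 99% interval 58.9% to 100%. Both rules pass with probability 1. Specificity among about 6 node-negative patients in a cohort would be 0/6 (99% interval 0 to 58.6%). Neither rule reads this.

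**4. A signal unrelated to disease.** Suppose a patient is a hit with probability 0.5 whatever the nodal status.

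- First rule, one cohort: P(X ≥ 2 of 10) = 0.989. Either cohort: 1 − (1 − 0.989)² > 0.999.
- Second rule: P(X ≥ 4 of 10) = 0.828.

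**5. The two definitions of a hit.** The fluorescence rates here are assumptions, as is the lower node count of 12.

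- Section 8.1 wording, 10% random fluorescence per node: P(at least one) = 1 − 0.9^12 = 0.72 with 12 nodes and 1 − 0.9^27 = 0.94 with 27. The second rule is then passed at least 99% of the time.
- Synopsis wording, 50% random fluorescence per node, 1 to 4 positive nodes per patient (assumed): P(hit) = 0.50 to 0.94. The second rule is passed 83% to over 99% of the time.

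**6. Node-negative patients at the chosen dose.** The expected share is 6/16 = 0.375.

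- Minimum second stage: 16 × 0.375 = 6.
- Largest second stage within 52 patients: (52 − 32) × 0.375 = 7.5.
- With the 6 first-stage patients at that dose: 12 to 13.5, so about 12 to 14.

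**7. What a specificity rule could do with 6 patients.** Compare two illustrative forms.

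| Form | Needs | True 78% fails | True 40% passes | True 0% passes |
|---|---|---|---|---|
| Observed specificity above 53% | ≥ 4/6 | 12.5% | 18% | never |
| Upper 99% bound at least 78% | ≥ 2/6 | 0.25% | 77% | never |

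For the second form the bound is 74.6% at 1/6 and 85.6% at 2/6. The failure chance at 78% is 0.22^6 + 6 × 0.78 × 0.22^5 = 0.0025. The pass chance at 40% is 1 − 0.6^6 − 6 × 0.4 × 0.6^5 = 0.767. The lenient form rarely rejects a good dose, but reliably stops only a grossly non-specific one.

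**The case against.** The other side has a good deal right, and three stronger readings should be set aside.

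- *A reader might infer that the dose is chosen on sensitivity alone.* It is not. Section 8.1 adds node-level information and practical considerations, and toxicity is recorded by dose. What remains is that no false-positive measure is named or required in that choice.
- *A reader might infer that node-negative patients serve only as a tumour-fluorescence control.* The sentence does not say so. Section 17 takes everyone who received 5-ALA as the primary analysis population. Appendix 3 maps every node as fluorescent or not and involved or not, and its example includes a fluorescent, uninvolved node. False positives will be recorded and can be described; they simply have no part in the rules.
- *A reader might infer that a non-specific dose would send patients to unnecessary surgery.* Not in this trial: under section 11.2 all participants have D3 lymphadenectomy whatever the fluorescence shows.

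The design point is stronger. The synopsis assigns sensitivity, specificity and diagnostic accuracy to the evaluation phase, and 8.1 presents the first rule as a sign of activity while techniques are still being optimised. A lenient early screen is legitimate. It is also true that if the starting dose shows activity, the second cohort receives a lower one, so the scheme does not simply chase more fluorescence. Nothing in the protocol predicts that every node would light up.

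This limits the harm but does not remove the gap. The dose is fixed in this phase, so the evaluation phase can reveal a non-specific dose but was not set up to choose another. Some non-specific signal is plausible: section 6.4 cites a nodal specificity of 78%, not 100%, for the endogenous signal. The rules are also fixed in the protocol, so this is not a detail left to an analysis plan.

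**Conclusion.** The point holds for the progression rules and the endpoints. Both rules are blind to false positives, section 15 defines no measure of them, and none is required in the dose choice. At the extreme of universal fluorescence both rules pass with certainty. At a hit probability of 0.5 unrelated to disease, the second is still passed 82.8% of the time with 10 patients.

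The certainty result needs no assumption beyond the written rules. The intermediate figures rest on the stated fluorescence rates and node counts, which the protocol does not give, and are illustrations rather than forecasts. The expected number of node-negative patients rests on the planned yield of 10 in 16.

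The consequence is a possibly wasted evaluation phase, not harm to participants here. It should be corrected, because the data are already collected; it does not invalidate the development phase.

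**What to change.** 1. **Section 15.** Add two descriptive endpoints, by dose and with exact intervals where a proportion is reported: per-patient specificity (no fluorescent node in a patient whose final histology is node-negative), and the number of false-positive nodes per patient.
2. **Sections 8.1 and 17.1.** State that both are considered together with sensitivity when the most promising dose is identified, and that the TSC and DMEC review them before progression to the evaluation phase.
3. **Any formal floor.** Keep it in the style of the existing rules: for example, do not progress if the upper 99% exact bound of specificity at the chosen dose lies below a target stated in advance. State whether first-stage patients at that dose count, since 8.1 excludes them from the sensitivity analysis. A hard cut on the observed proportion is not advisable with about 6 patients.
4. **Definition of a detection.** Reconcile 8.1 with the synopsis so that a fluorescent, uninvolved node cannot count as a hit.

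The cost is wording in the protocol and analysis plan, with no extra patients, procedures or data. The downside is an imprecise specificity estimate and, if a formal floor is adopted, a slightly higher chance of not progressing.
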